9.2.3. Figures

Figure 14.2.1.2.1: Spirometry: Subject profile plots over time

Subject profile plots over time for each parameter. Each treatment group will be on a new plot, with all subjects of the same treatment group on the same plot. Any unscheduled results will also be part of this plot.

The figure will show:

- OC in ITT.

Figure 14.2.1.2.2: Spirometry: Subject profile on change from baseline plot over time

Change from baseline subject profile plots over time for each parameter. Each treatment group will be on a new plot, with all subjects of the same treatment group on the same plot. Any unscheduled results will also be part of this plot.

The figure will show:

- OC in ITT.

Figure 14.2.1.2.3: Spirometry: Mean (+/- SE) plots of the actual values over time

Mean (with SE) plots of the actual values over time for each parameter. Unscheduled results will not be part of this plot.

The figure will show:

- LOCF in ITT.
- OC in ITT

Figure 14.2.1.2.4: Spirometry: Mean (+/- SE) plots of the changes from baseline over time

Mean (with SE) plots of the changes from baseline over time for each parameter. Unscheduled results will not be part of this plot. With a horizontal reference line at zero, indicating no change. Plots will start with a zero mean at baseline.

The figure will show:

- LOCF in ITT.
- OC in ITT

Figure 14.2.1.2.5: Spirometry: Sub-group analyses: Mean (+/- SE) plots of the changes from baseline over time

Mean (with SE) plots of the changes from baseline over time for each sub-group. Unscheduled results will not be part of this plot. With a horizontal reference line at zero, indicating no change. Plots will start with a zero mean at baseline.

The following sub-groups will be shown:

- By target C_{trough} at Day 15
- By target C_{trough} at Day 29
- By target C_{trough} at Day 15 and 29
- By sweat chloride (from arm with greatest volume) at baseline
- By sweat chloride (mean value from both arms) at baseline
- By %FEV1 at baseline

The figure will show:

- LOCF in ITT.
- OC in ITT

Figure 14.2.1.2.6: Spirometry: Pooled analyses: Mean (+/- SE) plots of the changes from baseline over time

Mean (with SE) plots of the changes from baseline over time on pooled treatment. Unscheduled results will not be part of this plot. With a horizontal reference line at zero, indicating no change. Plots will start with a zero mean at baseline.

The following sub-groups will be also provided in this pooled analysis:

- By target C_{trough} at Day 15
- By target C_{trough} at Day 29
- By target C_{trough} at Day 15 and 29

The table will show:

- LOCF in ITT.
- OC in ITT

Figure 14.2.1.2.7: Spirometry: Mean plots (+/- SE) of the percent changes from baseline over time

Mean (with SE) plots of the percent changes from baseline over time for each parameter. Unscheduled results will not be part of this plot. With a horizontal reference line at zero, indicating no change. Plots will start with a zero mean at baseline.

The figure will show:

- LOCF in ITT.
- OC in ITT

Figure 14.2.1.2.8: Spirometry: Boxplots on the actual values

Boxplots at each timepoint with all treatment groups in the same figure. Only for %FEV1 parameter.

The figure will show:

- LOCF in ITT.
- OC in ITT

Figure 14.2.1.2.9: Spirometry: Boxplots on the change from baseline

Boxplots at each timepoint for each treatment. Only for %FEV1 parameter.

The figure will show:

- LOCF in ITT.
- OC in ITT

9.2.4. Listings

Listing 16.2.6.2: Spirometry: Full listing

Listing per subject and per time point of all data related to spirometry: actual values, changes from baseline and percent changes from baseline.

The listing will show: ITT.

9.3. CYSTIC FIBROSIS QUESTIONNAIRE – REVISED (CFQ-R)

9.3.1. Parameters

The following scores will be derived from CFQ-R questionnaire:

- 9 Quality of life domains: Physical, role/school, vitality, emotion, social, body image, eating, treatment burden, health perceptions.
- 3 symptom scales: weight, respiratory and digestion.

Each Score will range from 0 to 100, with higher scores indicating better health.

For the analysis, the derivation of each score will be done with the following step for each time-point:

- Assigned a value for each questions (question 1 to question 50) with the following rules:

Questions	Categories	Score
Question 1 to 5	A lot of difficulty	1
	Some difficulty	2
	A little difficulty	3
	No difficulty	4
Question 6 to 12, 36 to 38, 44 to 50	Always	1
	Often	2
	Sometimes	3

	Never	4
Question 19 to 34	Very true	1
	Somewhat true	2
	Somewhat false	3
	Very false	4
Question 39 to 42	A great deal	1
	Somewhat	2
	A little	3
	Not at all	4
Question 13 to 18 and 35	1.XXXXXXX	1 = SUBSTR(qstresn,1,1)
	2.XXXXXXX	2 = SUBSTR(qstresn,1,1)
	3.XXXXXXX	3 = SUBSTR(qstresn,1,1)
	4.XXXXXXX	4 = SUBSTR(qstresn,1,1)
Question 43	Clear	4
	Clear to yellow	3
	Yellowish-green	2
	Green with traces of blood	1
	Don't know	5

- Items in the questionnaire are expressed either "negatively" or "positively," therefore a number of the items must be recoded before the scores for each of the domains are calculated. The following items (6, 10, 13, 15, 17, 18, 23, 28, 30, 32, 34, 35) should be recoded by using this formulae: new score = 5-score.
- Calculation of each score

Score	Formulae (Qx = Question x)
Physical	= (Mean(Q1, Q2, Q3, Q4, Q5, Q13, Q19, Q20) -1)/3*100 if at least 50% of the question have non-missing data
Role/school	= (Mean (Q35, Q36, Q37, Q38) - 1)/3*100 if at least 50% of the question have non-missing data
Vitality	= (Mean(Q6, Q9, Q10, Q11) -1)/3*100 if at least 50% of the question have non-missing data
Emotion	= (Mean(Q7, Q8, Q12, Q31, Q33) -1)/3*100 if at least 50% of the question have non-missing data
Social	= (Mean(Q22, Q23, Q27, Q28, Q29, Q30) -1)/3*100 if at least 50% of the question have non-missing data
Body image	= (Mean(Q24, Q25, Q26) -1)/3*100 if at least 2 questions have non-missing data
Eating	= (Mean(Q14, Q21, Q50) -1)/3*100 if at least 2 questions have non-missing data
Treatment burden	= (Mean(Q15, Q16, Q17) -1)/3*100 if at least 2 questions have non-missing data

Health perceptions	$= (\text{Mean}(Q18, Q32, Q34) - 1)/3 * 100$ if at least 2 questions have non-missing data
Weight	$= (Q39-1)/3 * 100$ if Q39 has non-missing value
Respiratory	$= (\text{Mean}(Q40, Q41, Q42, Q44, Q45, Q46) - 1)/3 * 100$ if at least 50% of the question have non-missing data
Digestion	$= (\text{Mean}(Q47, Q48, Q49) - 1)/3 * 100$ if at least 2 questions have non-missing data

- Select only score that correspond to a pre-dose assessment.

For each score, Analysis will present:

- Actual values
- Change from baseline (Day 1 pre-dose):
change at time point t = (time point t value) – (baseline value)
- Percent change from baseline (Day 1 pre-dose):
%change at time point t = $100 \times (\text{time point t value} - \text{baseline value}) / (\text{baseline value})$

9.3.2. Tables

Table 14.2.1.3.1: CFQ-R: Descriptive statistics of the actual values per time point

Descriptive statistics of actual values per treatment group and analysis visit for each score.

The table will show:

- LOCF in ITT.
- OC in ITT

Table 14.2.1.3.2: CFQ-R: Sub-group analyses: Descriptive statistics of the actual values per time point

Descriptive statistics of the actual values, treatment group and analysis visit for each sub-group analysis will be done only for CFQ-R respiratory domain score.

The following sub-groups will be shown:

- By target C_{trough} at Day 15
- By target C_{trough} at Day 29
- By target C_{trough} at Day 15 and 29
- By sweat chloride (from arm with greatest volume) at baseline
- By sweat chloride (mean value from both arms) at baseline
- By %FEV1 at baseline

The table will show:

- LOCF in ITT.
- OC in ITT

Table 14.2.1.3.3: CFQ-R: Pooled analyses: Descriptive statistics of the actual values per time point

Descriptive statistics of the actual values on pooled treatment group and analysis visit will be done only for CFQ-R respiratory domain score.

The following sub-groups will be also provided in this pooled analysis:

- By target C_{trough} at Day 15
- By target C_{trough} at Day 29
- By target C_{trough} at Day 15 and 29

The table will show:

- LOCF in ITT.
- OC in ITT

Table 14.2.1.3.4: CFQ-R: Descriptive statistics of the changes from baseline per time point

Descriptive statistics of changes from baseline per treatment group and analysis visit for each score. The actual value at baseline will also be presented in this table.

P-values are generated from an ANCOVA model on the changes from baseline at each time point with treatment as factors and baseline value as covariate. Pairwise comparison (dose group vs placebo) will be provided as well.

P-values will be generated also from a Kruskal-Wallis test (overall treatment effect) and Wilcoxon rank sum test (pairwise comparison with placebo) as sensitivity analysis.

The table will show:

- LOCF in ITT.
- OC in ITT (only descriptive, no inferential statistics)

Table 14.2.1.3.5: CFQ-R: Descriptive statistics of the changes from baseline per time point on Placebo groups

Descriptive statistics of changes from baseline per cohort, per treatment group and analysis visit. The actual value at baseline will also be presented in this table.

Descriptive statistics of changes from baseline per cohort, analysis visit on placebo (cohort A), on placebo (cohort B), on pooled placebo. The actual value at baseline will also be presented in this table.

The table will show:

- LOCF in ITT.
- OC in ITT

Table 14.2.1.3.6: CFQ-R: Sub-group analyses: Descriptive statistics of the changes from baseline per time point

Descriptive statistics of changes from baseline, treatment group and analysis visit for each sub-group analysis will be done only for CFQ-R respiratory domain score. The actual value at baseline will also be presented in this table.

The following sub-groups will be shown:

- By target C_{trough} at Day 15
- By target C_{trough} at Day 29
- By target C_{trough} at Day 15 and 29
- By sweat chloride (from arm with greatest volume) at baseline
- By sweat chloride (mean value from both arms) at baseline
- By %FEV1 at baseline

The table will show:

- LOCF in ITT.
- OC in ITT

Table 14.2.1.3.7: CFQ-R: Pooled analyses: Descriptive statistics of the changes from baseline per time point

Descriptive statistics of changes from baseline per pooled treatment group and analysis visit will be done only for CFQ-R respiratory domain score. The actual value at baseline will also be presented in this table.

The following sub-groups will be also provided in this pooled analysis:

- By target C_{trough} at Day 15
- By target C_{trough} at Day 29
- By target C_{trough} at Day 15 and 29

The table will show:

- LOCF in ITT.
- OC in ITT

Table 14.2.1.3.8: CFQ-R: Descriptive statistics of the percent changes from baseline per time point

Descriptive statistics of percent changes from baseline per treatment group and analysis visit for each score. The actual value at baseline will also be presented in this table.

The table will show:

- LOCF in ITT.
- OC in ITT

Table 14.2.1.3.9: CFQ-R: Sensitivity analyses on the changes from baseline values

Additional sensitivity analysis will be explored by using Mixed Effects Model for Repeated Measures (MMRM). The model will include treatment and analysis visit as fixed effects and baseline as a covariate, treatment*analysis visit as interaction terms and subject as random effect for each score. Pairwise comparisons will be presented.

The table will show:

- OC in ITT.

9.3.3. Figures

Figure 14.2.1.3.1: CFQ-R: Subject profile plots over time

Subject profile plots over time for each score. Each treatment group will be on a new plot, with all subjects of the same treatment group on the same plot. Any unscheduled results will also be part of this plot.

The figure will show:

- OC in ITT.

Figure 14.2.1.3.2: CFQ-R: Subject profile on change from baseline plot over time

Change from baseline subject profile plots over time for each score. Each treatment group will be on a new plot, with all subjects of the same treatment group on the same plot. Any unscheduled results will also be part of this plot.

The figure will show:

- OC in ITT.

Figure 14.2.1.3.3: CFQ-R: Mean (+/- SE) plots of the actual values over time

Mean (with SE) plots of the actual values over time for each score. Unscheduled results will not be part of this plot.

The figure will show:

- LOCF in ITT.
- OC in ITT

Figure 14.2.1.3.4: CFQ-R: Mean (+/- SE) plots of the changes from baseline over time

Mean (with SE) plots of the changes from baseline over time for each score. Unscheduled results will not be part of this plot. With a horizontal reference line at zero, indicating no change. Plots will start with a zero mean at baseline.

The figure will show:

- LOCF in ITT.
- OC in ITT

Figure 14.2.1.3.5: CFQ-R: Sub-group analyses: Mean (+/- SE) plots of the changes from baseline over time

Mean (with SE) plots of the changes from baseline over time for each sub-group will be done only for CFQ-R respiratory domain score. Unscheduled results will not be part of this plot. With a horizontal reference line at zero, indicating no change. Plots will start with a zero mean at baseline.

The following sub-groups will be shown:

- By target C_{trough} at Day 15

- By target C_{trough} at Day 29
- By target C_{trough} at Day 15 and 29
- By sweat chloride (from arm with greatest volume) at baseline
- By sweat chloride (mean value from both arms) at baseline
- By %FEV1 at baseline

The figure will show:

- LOCF in ITT.
- OC in ITT

Figure 14.2.1.3.6: CFQ-R: Pooled analyses: Mean (+/- SE) plots of the changes from baseline over time

Mean (with SE) plots of the changes from baseline over time on pooled treatment will be done only for CFQ-R respiratory domain score. Unscheduled results will not be part of this plot. With a horizontal reference line at zero, indicating no change. Plots will start with a zero mean at baseline.

The following sub-groups will be also provided in this pooled analysis:

- By target C_{trough} at Day 15
- By target C_{trough} at Day 29
- By target C_{trough} at Day 15 and 29

The table will show:

- LOCF in ITT.
- OC in ITT

Figure 14.2.1.3.7: CFQ-R: Mean plots (+/- SE) of the percent changes from baseline over time

Mean (with SE) plots of the percent changes from baseline over time for each score. Unscheduled results will not be part of this plot. With a horizontal reference line at zero, indicating no change. Plots will start with a zero mean at baseline.

The figure will show:

- LOCF in ITT.
- OC in ITT

9.3.4. Listings

Listing 16.2.6.3: CFQ-R: Full listing

Listing per subject and per time point of all data related to CFQ-R: actual values, changes from baseline and percent changes from baseline.

The listing will show: ITT.

10. DEFINITIONS OF PHARMACOKINETICS ANALYSIS TABLES, LISTINGS AND FIGURES

- Compounds:
 - GLPG2222
- PK parameters are:
 - C_{max} , t_{max} , C_{trough} , AUC_{0-t}
 - $C_{max}/dose$, $C_{trough}/dose$, $AUC_{0-t}/dose$

C_{max}	Maximum concentration after multiple dosing (ng/mL), obtained directly from the observed concentration versus time data.
t_{max}	Time of occurrence of maximum concentration after multiple dosing (h), obtained directly from the observed concentration versus time data.
C_{trough}	Plasma concentration observed at pre-dose (ng/mL), obtained directly from the observed concentration versus time data.
AUC_{0-t}	Area under the concentration-time curve up from time 0 up to 24 h following multiple dosing (ng·h/mL), calculated by linear up/log down trapezoidal summation.

On Day 15, all PK parameters will be determined (or on Day 29 if the subject is not available for full PK profiling on Day 15). On Day 29, only C_{trough} will be determined.

10.1.1. PK Parameter Derivation Rules

Pharmacokinetic analysis of the plasma concentration data for GLPG2222 will be performed at [REDACTED], United States. PK parameters will be derived using standard non compartmental methods using Phoenix WinNonlin® 6.4 or higher (Pharsight Corp., Certara Company, Princeton, New Jersey, United States); and/or SAS® Version 9.4 or higher. Graphics may be prepared with SAS® Version 9.4, or higher; SigmaPlot® 12.5, or higher (Systat Software, Inc., San Jose, California, United States); or Phoenix WinNonlin® 6.4, or higher. For PK analysis, the following rules will be applied:

- BLOQ concentration will be imputed according to the rules mentioned in Section 5.3.2
- If the concentrations before and after a quantifiable timepoint are below the limit of quantification, the quantifiable timepoint will not be included in the PK analysis.
- Plasma concentrations that again become quantifiable at time points after being BLOQ at earlier time points will be excluded from analysis at those time points.
- Subjects with less than 3 concentrations $>$ LOQ are excluded from that day.
- Day 15 (or Day 29) 24h post-dose plasma concentrations will be imputed using the pre-dose value, in order to complete the full dosing interval PK profile (of 24 hours).
- Exposures will be calculated according to linear up/log down trapezoidal method using theoretical sampling time points.

- Theoretical sampling time will be used for PK parameters calculation, except if the deviation of actual sampling time is >10%, when the actual sampling time will be used.

Handling of other potential anomalies in the plasma PK profiles will be discussed with Galapagos before PK parameter derivation.

Excluded data will be flagged in the TLFs.

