6.5. PHARMACOKINETICS ASSESSMENTS

6.5.1. Blood Samples

Blood samples will be collected during the treatment period for the determination of GLPG2222 in plasma at the following time points:

- Day 15: pre-dose and 0.5, 1, 2, 3, 4, 6 and 8 hours post-dose;
 - If it is known upfront that the subject is not available for the ‘full’ PK profiling on Day 15, it is allowed to schedule and perform this PK profiling on Day 29.
- Day 29: pre-dose;
- ED (if applicable): one additional sample to be taken pre-dose if study drug is still taken, or at any time during the visit if study drug is no longer taken.

Plasma concentrations of GLPG2222 will be measured using a validated liquid chromatography tandem mass spectrometry method with a lower limit of quantification of 1.00 ng/mL. The details of sample handling and shipment instructions will be provided in a separate laboratory manual.

After the study is completed, any left-over samples belonging to the study subject may be stored for a period of 5 years under the control of the sponsor. These samples may be used by the sponsor or sponsor’s partner, or by other companies belonging to the sponsor for additional PK investigation (i.e. metabolic profiling, which is the assessment of biochemical intermediates – metabolites - in blood in order to describe the metabolic pathway of the compound). No characterization of human genetic material will be undertaken. Specific consent for storage of samples should be obtained from the subjects. Any research outside the context described in this protocol may only be conducted after approval by the IEC(s)/IRB(s) and Regulatory Authority.

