¹⁰ Serology sample for hepatitis B virus surface antigen, hepatitis C virus antibody and human immunodeficiency type 1 and 2 antibodies.

¹¹ For female subjects of childbearing potential only; serum pregnancy test at screening, urine pregnancy test at other scheduled visits.

¹² For suspected post-menopausal female subjects only (age < 55 years and no menses for ≥ 12 months without a medical cause).

¹³ PK blood samples for GLPG2222 to be taken pre-dose and 0.5, 1, 2, 3, 4, 6 and 8 hours post-dose on Day 15 (or on Day 29 if subject is not available for full PK profiling on Day 15), and pre-dose on Day 29. In case of an early discontinuation visit, one additional sample to be taken pre-dose if study drug is still taken, or at any time during the visit if study drug is no longer taken.

¹⁴ Exploratory biomarkers [REDACTED].

¹⁵ Study drug to be taken once daily in the morning with a breakfast or snack.

¹⁶ Only for subjects who give separate consent to participate in the optional substudy.

AE = adverse event; CFTR = cystic fibrosis transmembrane conductance regulator; FSH = follicle stimulating hormone, PK = pharmacokinetic(s)

EVENT	SCREENING	TREATMENT PERIOD ¹				FOLLOW-UP
		D1	D15 (±2D)	D29 (±2D)	ED	
Study days (D)	D-28 till D-1					
Nasal brushing		X	X	X		

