10.1.2. Tables

Table 14.2.2.1: GLPG2222 Trough plasma concentrations (ng/mL): Individual data and descriptive statistics per dose and day

Subject data with descriptive statistics per dose, day of the predose plasma concentrations (Day 15, Day 29).

Compound: GLPG2222.

Population: PK.

Table 14.2.2.2: GLPG2222 Plasma concentrations (ng/mL): Individual data and descriptive statistics per dose level on the day of the full PK profile

Subject data with descriptive statistics per dose on the day of the full PK profile (PK profile data from day 15 and Day 29 will be pooled).

Compound: GLPG2222.

Population: PK.

Table 14.2.2.3: GLPG2222 PK parameters: Individual data and descriptive statistics per dose on the day of the full PK profile

Subject data with descriptive statistics per dose of the derived PK parameters (C_{max} , t_{max} , C_{trough} , AUC_{0-t} , $C_{max}/dose$, $C_{trough}/dose$, $AUC_{0-}/dose$) on the day of the full PK profile (PK profile data from day 15 and Day 29 will be pooled).

Compound: GLPG2222.

Population: PK.

Table 14.2.2.4: GLPG2222 PK parameters: statistical assessment of dose-proportionality

Dose proportionality of PK parameters C_{max} , AUC_{0-t} , C_{trough} (Day 15) and C_{trough} (Day 29) will be assessed statistically using the power model approach. The power model will be:

$\log(\text{parameter}) = \alpha + \beta * \log(\text{dose})$ where ' α ' is the intercept and ' β ' is the slope.

Prior to the analysis, the assumption of a linear relationship between the $\log AUC_{0-t}$ (C_{max} , C_{trough} (Day 15) and C_{trough} (Day 29)) and log-dose was tested using analysis of variance by partitioning the sums of squares for treatments into those for linearity and departures from

linearity. If the departures from linearity were significant then the hypothesis of dose proportionality was rejected and the power model analysis was not performed.

The estimate obtained for β is a measure of dose proportionality. The estimate of β together with its 90% CI (β_l, β_u) was presented to quantify the degree of non-proportionality.

The intercept α and the slope β together with 90% CIs will be estimated and presented for each PK parameter. The power model parameters will be estimated using least-squares (LS) regression or an equivalent method. A minimum of 3 values per dose must be available for a given parameter to estimate dose proportionality with the power model.

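### Does the SAP's rule on fewer than three quantifiable concentrations throw away the single Day 29 trough sample?

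*SAP*

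**What the plan says.** The rule is one bullet in SAP section 10.1.1 (PK Parameter Derivation Rules). The list is introduced by "For PK analysis, the following rules will be applied". The bullet begins "Subjects with less than 3 concentrations" and, after the symbol for exceeding the quantification limit, ends "LOQ are excluded from that day". It names no particular day.

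Protocol section 6.5.1 schedules eight samples on Day 15 (pre-dose and seven post-dose times), and then "Day 29: pre-dose". Footnote 13 of the SAP flow chart says the same and allows the full profile to be moved: "or on Day 29 if subject is not available for full PK profiling on Day 15), and pre-dose on Day 29".

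SAP section 10 lists C_trough among the PK parameters and states "On Day 29, only C_{trough} will be determined". In SAP section 10.1.2, Table 14.2.2.4 includes the Day 29 trough among the parameters for dose proportionality ("Day 29) will be assessed statistically using the power model approach"), subject to a data requirement: "A minimum of 3 values per dose must be available for a given parameter to estimate dose proportionality with the power model". Table 14.2.2.1 summarises the pre-dose concentrations of both days. SAP section 5.3.2 has its own rule for troughs below the quantification limit: they enter inferential statistics as half that limit.

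**The concern.** The exclusion bullet and the planned Day 29 output cannot both be followed to the letter. A subject profiled on Day 15 has at most one quantifiable concentration on Day 29, so a threshold of three excludes that subject from Day 29 whatever the measured value. C_trough is a listed PK parameter, so the section heading does not by itself take it outside the rule, and no sentence exempts a day with only a trough sample.

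The output most clearly at stake is the Day 29 trough part of Table 14.2.2.4: the power-model slope and the derived increase for a doubling of dose. The Day 29 parts of Table 14.2.2.1 and Figures 14.2.2.1 and 14.2.2.2 are less clearly reached, because they show observed pre-dose concentrations. The sub-groups by Day 29 target trough in SAP section 3.4 would be touched only if they were built from the derived parameter. PK parameters are a secondary endpoint. The primary safety endpoint is not involved.

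**Working it through.** The plan gives no figure of its own on this point. The check is a count under each reading, followed by a comparison of the passages.

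**Inputs**
- Scheduled samples on a full-profile day: 8 (Protocol 6.5.1).
- Scheduled samples on Day 29 for a subject profiled on Day 15: 1 (Protocol 6.5.1; SAP flow chart footnote 13).
- Exclusion threshold: fewer than 3 quantifiable concentrations (SAP 10.1.1).
- Planned size: 25 per cohort, randomized 2:2:1, two active doses per cohort (Protocol 5.1).
- Minimum for the power model: 3 values per dose (SAP 10.1.2).

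**Literal reading**
- Planned subjects per active dose: 25 × 2/5 = 10. Over four doses: 4 × 10 = 40.
- Day 29 after a Day 15 profile: 1 < 3, so the subject is always excluded from that day.
- With no profile moved to Day 29: 40 − 40 = 0 troughs left, 0 per dose against 3 needed.
- Fewest moved profiles that would meet the minimum at every dose: 3 × 4 = 12, and 12/40 = 30%.
- The documents do not give the share moved. Assuming each subject moves independently with probability q, the chance that one dose keeps at least 3 of 10 values is P(X ≥ 3), X ~ Binomial(10, q). This is 1.2% at q = 5%, 7.0% at 10%, 32.2% at 20% and 61.7% at 30%.

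So the literal reading would normally leave the Day 29 power model without usable input.

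**Full-profile reading**
- Day 29 troughs available: up to 10 per dose, 40 in all. Since 10 ≥ 3, the minimum is met.

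**Which reading the text supports**
1. The list follows a statement that parameters are derived by standard non-compartmental methods.
2. The two bullets before the rule deal with quantifiable values next to, or after, unquantifiable ones in a time series. The two after it fill in the 24-hour point from the pre-dose value and compute exposure by the trapezoidal method. A minimum number of points placed between them is a minimum for a curve.
3. The threshold has a purpose for C_max, t_max and AUC, which need several points. It has none for a trough, which is one observation by definition.
4. SAP section 10 and Table 14.2.2.4 name the Day 29 trough specifically. The literal rule would leave them with almost no data. It would also drop a fully quantifiable Day 29 trough, while section 5.3.2 keeps an unquantifiable one at half the limit.

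Points 1 to 3 indicate a profile rule. Point 4 shows that the other reading defeats specific instructions in the same SAP.

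**The case for a change.** The strongest case for a change is that a SAP should be executable without the analyst having to depart from a written rule, and that this one states the limit elsewhere. Tables 14.2.2.2 and 14.2.2.3 are expressly confined to the day of the full profile, and the bullet is not. In addition, the first bullet of the list refers to section 5.3.2, which contains a rule for troughs, so the list is not purely about profiles. One clause would settle the matter at almost no cost.

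It stands that the scope is unstated. The inference that a wider scope was intended does not. The bullet on trapezoidal exposure also carries no day limit, yet it can apply only to a profile, so leaving the limit out is how this list is drafted. The reference to section 5.3.2 concerns imputation of unquantifiable values, not who is excluded.

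A smaller question remains. On a profile day with fewer than 3 of the 8 samples quantifiable, the text does not say whether the pre-dose value is dropped together with C_max, t_max and AUC. How often this would happen cannot be worked out from the documents. Any such exclusion would be visible, because section 10.1.1 requires excluded data to be flagged and Listing 16.2.7.1 records each data issue and its handling.

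**Conclusion.** The concern does not call for a change. The loss of 40 out of 40 planned Day 29 troughs arises only if the bullet is applied to days for which it was evidently not written and if no profile is moved to Day 29. On the reading that the heading, the neighbouring bullets and the specific Day 29 instructions support, up to 10 troughs per dose remain and Table 14.2.2.4 can be produced as planned.

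There is no plausible route to a wrong reported result. Either the troughs are analysed as section 10 and Table 14.2.2.4 direct, or the Day 29 model has too few values and the flagged exclusions show why. A scope clause would be harmless tidying, but no estimate or conclusion would be expected to differ.

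This conclusion assumes planned enrolment, scheduled sampling only, and an analyst who reads the rule list together with the tables it serves.
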